## 7 HANDLING OF MISSING VALUES

Missing observations will be treated as missing except for dates. For dates with missing days but not missing months, the 1st of the month will be imputed, and for dates with missing months and days, July will be imputed for months and the 15th will be imputed for days.

For any missing data (CCI [REDACTED]) corresponding to PRO, the PRO specific scoring manual will be utilized for imputation.

Patients with missing data for a variable will be excluded from the denominator when calculating proportions involving observed data for that variable.

If the tafamidis start day is missing, it will be imputed as the 15th of the corresponding month as per the eCRF guidelines. For date of birth, if only year is collected, then the day and month will be considered as 1st of January.

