### 9.3.1. Study Assessments

- Written informed consent/assent.
- Inclusion/exclusion criteria.
- Patient demographics (year of birth, gender, ethnic origin, race (if allowed by local regulations)).
- TTR genetic test results.
- Family disease history (previous family history of ATTR amyloidosis).

- Medical history (past and current signs, symptoms, and medical diagnoses).
- Annual medical assessment (current signs and symptoms).
- General examination (weight/height, vital signs, CCI [REDACTED]).
- Concomitant medications (category, indication, start and stop dates).
- Hospitalizations (admission and discharge dates, reason for hospitalization).
- Transplant history and complications (date(s) of transplant(s), organ(s) transplanted, information on complications).
- AE/SAE reporting for tafamidis-treated subjects.
- Events of interest (as listed in Table 1, Summary of Safety Concerns to be Assessed in THAOS).
- Clinical laboratory data (hematology, clinical chemistry, liver function tests, thyroid function tests).
- Urinalysis (includes glomerular filtration rate [GFR]).
- Cardiovascular assessments (electrocardiogram, echocardiogram, Holter monitoring, CCI [REDACTED]).
- Neurologic assessments (deep tendon reflexes, sensation [pinprick, soft touch, vibration, and position sense], motor strength, nerve conduction studies).
- Eye examination (intraocular pressure, vitreous, presence of opacities).
- Body composition (total bone mineral density and content, total lean and fat mass).
- CCI [REDACTED]
- Patient death (data on patient death will be collected independently of the visit schedule).

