#### **6.2.1 Survival**

Survival will be analysed as time from enrollment or first dose of tafamidis, for the untreated and tafamidis treated set respective until the time of death. Patients who are still alive at the end of the analysis period (start of tafamidis or end of follow-up in THAOS for the untreated set or last dose of tafamidis in the tafamidis treated set) will be censored.

CCI [Redacted]

[Redacted]

[Redacted]

[Redacted]

- [Redacted]
- [Redacted]
- [Redacted]

CCI [Redacted]

[Redacted]

[Redacted]

[Redacted]

PFIZER CONFIDENTIAL

[Redacted]

CCI

[Redacted]

[Redacted]

[Redacted]

CCI

[Redacted]

[Redacted]

[Redacted]

[Redacted]

[Redacted]

CCI

[Redacted]

[Redacted]

PFIZER CONFIDENTIAL

[Redacted]

CCI [Redacted]

CCI [Redacted]

[Redacted]

[Redacted]

[Redacted]

[Redacted]

[Redacted]

[Redacted]

- [Redacted]
- [Redacted]
- [Redacted]
- [Redacted]

PFIZER CONFIDENTIAL

[Redacted]

CCI [Redacted]

[Redacted]

[Redacted]

[Redacted]

- [Redacted]
- [Redacted]
- [Redacted]
- [Redacted]
- [Redacted]
- [Redacted]

[Redacted]

- [Redacted]
- [Redacted]

[Redacted]

[Redacted]

CCI [Redacted]

[Redacted]

[Redacted]

[Redacted]

CCI [REDACTED]

CCI [REDACTED]

CCI [REDACTED]

[REDACTED]

[REDACTED]

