### 8.2.2 Baseline demographics

Summaries of baseline demographic will include the following:

Gender, age at enrollment, race/ethnicity, country of birth, country of residence, country of origin, duration of ATTR amyloidosis symptoms at enrollment, time from symptom onset to diagnosis, age at onset of symptoms, follow-up time.

Summaries will be provided for the following sets: all enrolled patients, tafamidis treated set by phenotype at enrollment and overall, tafamidis untreated set by phenotype at enrollment and overall.

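### SAP Section 7 sets partial dates to fixed days without checking them against known dates, so an imputed death can precede enrollment or first dose and an imputed onset can follow diagnosis

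*SAP*

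**What the plan says.** SAP Section 7 leaves missing observations as missing, except dates. It gives four date rules.

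- Day missing, month known: "For dates with missing days but not missing months, the 1"st of that month is used.
- Month and day missing: "for dates with missing months and days, July will be imputed for months", with the 15th as the day.
- Tafamidis start: "If the tafamidis start day is missing, it will be imputed as the 15"th of the month.
- Birth: "For date of birth, if only year is collected, then the day and month will be considered as" 1 January.

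The first two rules are general. Death, symptom onset and diagnosis dates are neither named nor exempted. The readable text does not limit an imputed date by consent, first dose, last contact, diagnosis or birth. The redaction inside Section 7 concerns patient-reported outcomes only. Protocol 9.8.1 describes automatic checks, but on data as entered, not on dates created at analysis.

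These dates feed several outputs. SAP 6.2.1 states: "Survival will be analysed as time from enrollment or first dose of tafamidis", ending at death. SAP 8.2.2 lists "time from symptom onset to diagnosis, age at onset of symptoms, follow-up time" among the baseline summaries. SAP 8.2.4 decides whether a symptom developed after baseline by comparing its onset date with enrollment (untreated set) or first dose (treated set).

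**The concern.** A fixed-day rule is harmless when the reference date is years away. It fails when the partial date shares a year or month with the date it is measured from. A patient who consented in October and died that December, with only the year of death recorded, is given a July death and a negative survival time. A negative time has no valid place in a Kaplan-Meier estimate, and the SAP does not say what to do with it, so someone would have to decide after seeing the data.

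SAP 8.2.6 plots mortality for subgroups such as severe hepatic impairment at baseline and liver transplant status. SAP 8.1 gives estimates only when there are at least 5 events. In such a group one mishandled death can change the curve, or whether an estimate is shown at all. For natural history, an onset dated after diagnosis yields an impossible negative delay, and SAP 8.1 reports minimum and 10th percentile, where such values would show.

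**Working it through.** The plan states no figure on this point, so there is none to reproduce. Inputs are the Section 7 rules. I take a 365-day year, in which 15 July has 195 days before it and 169 after it, and treat all ordered date pairs as equally likely. The number of same-year ordered pairs is 365 × 366 / 2 = 66,795.

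**Death and enrollment**

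- *Same year, death year-only.* The imputed death precedes enrollment whenever enrollment is after 15 July: (169 × 170 / 2) / 66,795 = 14,365 / 66,795 = 21.5%.
- *Same month, death day missing.* The 1st precedes enrollment unless enrollment was on the 1st. In a 30-day month there are 30 × 31 / 2 = 465 ordered pairs, of which 30 start on the 1st: 435 / 465 = 93.5%.
- *Same month as tafamidis start, both days missing.* Start becomes the 15th and death the 1st, so death is always 14 days before first dose.

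**Onset and diagnosis, same year**

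- Onset year-only, diagnosis fully dated: onset falls after diagnosis whenever diagnosis is before 15 July, (195 × 196 / 2) / 66,795 = 19,110 / 66,795 = 28.6%.
- Diagnosis year-only, onset fully dated: 21.5%, by the same count as for deaths.

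**Onset and enrollment, same month, onset day missing.** The 1st is never later than the enrollment date, so such a symptom can never count as developed after enrollment, even if it was.

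**Overall size, deaths.** The documents give neither the share of partial dates nor the survival distribution. Assume that every death is year-only, enrollment is uniform over the year, survival is exponential with median m, and every patient is followed to death. With c = 195/365 = 0.534 and λ = ln 2 / m, the share dated before enrollment is (1 − c) − [1 − exp(−λ(1 − c))] / λ.

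| Assumed median survival (years) | Share of deaths before enrollment |
|---|---|
| 3 | 2.4% |
| 5 | 1.5% |
| 10 | 0.7% |
| 15 | 0.5% |

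With censoring, early deaths make up more of the recorded deaths. If everyone's follow-up stopped at one median, half would have died and the shares would double, to about 1.0% to 4.8%. In practice only some deaths would be year-only, which lowers the figure in proportion.

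**Overall size, onset.** Assume that every onset is year-only and diagnosis fully dated, with onset uniform over the year and exponential delay. The share dated after diagnosis is c − [1 − exp(−λc)] / λ: about 16%, 8.8%, 4.7% and 2.4% at assumed median delays of 0.5, 1, 2 and 4 years.

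**Births.** With births uniform over the year, 1 January adds on average (364 / 2) / 365.25 = 0.498 year to exact age, with a range of 0 to 0.997. Using 1 July leaves a mean excess of 0.003 year.

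**The case against.** A reader might infer that some deaths in this registry do precede enrollment, that some onsets do follow diagnosis, and that everyone's age runs half a year high. The documents do not support that.

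- **Partial dates are not counted.** The rules permit these errors but do not show them. The 22% and 29% apply only to partial dates in the same year as the reference date.
- **Death dates should be fairly complete.** Deaths are recorded independently of the visit schedule (Protocol 9.3.1). Sites are asked for all available information on a death (9.3.6), and fatal serious events in tafamidis-treated patients are notified immediately (11.1). This makes year-only deaths less likely, though it does not govern those that remain.
- **The delay summary barely moves.** With every onset year-only, setting negative delays to zero raises the mean by 10.8, 5.9, 3.1 and 1.6 days at assumed median delays of 0.5, 1, 2 and 4 years, and leaves the median unchanged. What remains is impossible values in the lower tail.
- **Birth year only for everyone is not established.** Protocol 9.3.1 has "Patient demographics (year of birth, gender, ethnic origin, race" but SAP Table 2 lists full date of birth, and the Section 7 rule is conditional. The size also depends on an age derivation that the SAP does not state. In completed years, the 1 January rule gives enrollment year minus birth year. Its mean matches mean exact age and is 0.5 high only against true completed age.
- **Mid-year births have a cost.** With 1 July, about 12% of true 18-year-olds with year-only births would compute as under 18 (uniform dates), creating apparent breaches of the age criterion in Protocol 9.2.1. The 1 January rule never does this.
- **All analyses are descriptive** (SAP Section 4), so no test is at risk.

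These points limit the size of the problem. They do not supply the missing order check.

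**Conclusion.** The concern holds as a faulty stated rule with a probably small effect. Followed literally, Section 7 can date a death before enrollment or first dose and an onset after diagnosis. It also keeps any onset without a day in the enrollment month from counting as post-enrollment. The clash between the 1st and the 15th makes one error certain whenever its conditions are met.

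The conditional shares (about 22%, 93% and 29%) rest on equally likely dates. The overall figure of about 0.5% to 2.4% of deaths also assumes that all deaths are year-only, survival is exponential with medians of 15 to 3 years, and follow-up is complete. It rises with censoring and falls with the true share of year-only deaths. The practical risk lies in the small mortality subgroups near the 5-event threshold. One might also infer that software would silently drop such deaths, but the documents specify neither software nor handling. The supported point is that handling is undefined.

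The birth rule is secondary: an average overstatement of about 0.5 year, only where the year alone is held. This assessment covers the readable text; a redacted part of the SAP could hold a further rule.

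**What to change.** Add to SAP Section 7:

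1. After imputation, a death date may not precede the last date known alive (consent, visit, dose or assessment).
2. Onset and diagnosis dates are bounded by birth, by each other and by the date of the form that recorded them.
3. The rules for a missing tafamidis start day and for other missing days are reconciled, so that events in the same month are not forced before first dose.
4. The numbers of imputed death, onset and diagnosis dates are reported.

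Violations against known dates then fall to zero by construction, and the reported counts supply the magnitude that the documents lack.

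Secondary: for year-only births, use mid-year in the descriptive age summaries only, not for checking the criterion of age 18 or over; or keep 1 January and state the bias with the table.

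The cost is a few sentences and derivation lines, with no new data. If mid-year births are adopted, mean exact age for those patients drops by about half a year, and two birth conventions must be kept apart in programming.

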### **Exposure**

Duration of exposure (in years) among patients receiving tafamidis while enrolled in THAOS will be summarized (excluding time when the patient was part of clinical trial or Compassionate Use/Early Access Program) by starting dose using the tafamidis treated set by phenotype at enrollment and overall, CCI [REDACTED] and either predominantly cardiac or mixed phenotype at enrollment, tafamidis treated set for patients who had severe hepatic impairment at baseline, tafamidis treated set by liver transplantation status (liver transplant prior to first dose of tafamidis/liver transplant after the first dose of tafamidis/no liver transplant).

Additionally the duration of treatment with 20 mg and 61 mg/80 mg will be summarized separately for patients with off label use.

The duration of exposure (in years) will be calculated as:

Sum of all non-missing days when tafamidis was taken (excluding days of other clinical trial/compassionate use participation) / 365.25

Summary of exposure-adjusted Incidence rates (per patient-year) AEs and SAE for Treatment Emergent Adverse events (All causalities) and mortality for tafamidis treated set will be provided.

A separate listing will be provided for duration of exposure listing for patients who switched from 61/80 mg to 20 mg.

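### SAP Section 7 dates an onset with a missing day before first dose when it falls in the month tafamidis was started

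*SAP*

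**What the plan says.** SAP Section 7 gives three date rules that bear on this point.

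- "For dates with missing days but not missing months", the 1st is used.
- With month and day both missing, the date becomes 15 July.
- "If the tafamidis start day is missing, it will be imputed as the" 15th of that month. The SAP attributes this rule to the eCRF guidelines.

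The visible text makes no exception for onset, admission or stop dates. It does not say that an imputed onset may not precede first dose.

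These dates feed the following definitions and analyses:

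- SAP 5.3: for patients who start tafamidis after enrollment, the treated set opens at first dose. For patients already on tafamidis it opens at enrollment.
- SAP 5.2: data from before the first dose belong to the untreated set.
- SAP 8.2.4: a post-baseline symptom in the treated set must begin after the first dose.
- SAP 8.2.6, Exposure: announces a "Summary of exposure-adjusted Incidence rates (per patient-year) AEs and SAE for Treatment Emergent Adverse events" for the treated set. The visible SAP does not define treatment-emergent.
- SAP 8.2.6, Hospitalization: summaries for both the treated and the untreated set.
- SAP 8.2.6, Adverse Events: summaries for the treated set and its subgroups only, plus an adverse event listing for all enrolled patients.

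**The concern.** Whether an event counts as on treatment depends on comparing two dates, and the imputation pushes them apart. An onset with a missing day goes to the earliest day of its month. First dose stays where it was recorded or goes to mid-month. A partly dated onset in the start month is therefore nearly always classed as pre-dose, whatever actually happened.

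The consequence differs by outcome. A displaced adverse event has no untreated summary to appear in and survives only in the all-enrolled listing. A displaced symptom or hospitalization leaves the treated summary and enters the untreated one, so both are distorted. If enrollment falls in the same month, the imputed date may precede enrollment as well, and the event can then drop out of both.

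This is a post-authorisation safety study, so treatment-emergent counts are a main product. Protocol 11.2 also opens safety reporting at first dose (or at consent if already treated). Many recorded adverse events should therefore be on treatment, and dating them before first dose conflicts with the collection window.

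**Working it through.** The study is descriptive, so there is no planned figure to reproduce. The check applies the Section 7 rules literally.

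**Inputs.** Missing day → 1; missing month and day → 15 July; missing tafamidis start day → 15 (all SAP 7). The treated window opens at first dose for patients who start after enrollment (SAP 5.3). Study day = date − first dose + 1 (SAP Appendix 2).

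**Assumption, not in the documents.** Start day s and onset day e are uniform and independent within a month of L days. Truly post-dose means e ≥ s.

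**1. Both days missing, same month.** 1 − 15 = −14 days, which is study day −13. The true days play no part, so 100% of truly post-dose events are misdated.

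**2. Start day known, onset day missing.** There are L(L+1)/2 post-dose pairs. Only the L pairs with s = 1 escape, so the misdated share is [L(L+1)/2 − L] / [L(L+1)/2] = (L−1)/(L+1).

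| L | Misdated / post-dose pairs | Share |
|---|---|---|
| 28 | 378 / 406 | 93.1% |
| 30 | 435 / 465 | 93.5% |
| 31 | 465 / 496 | 93.8% |

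The pairs that escape are ties with the first-dose date. The symptom rule in 8.2.4 asks for onset strictly after first dose, so it excludes those too.

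**3. Onset month and day missing, start date known, same year.** 15 July is day 196 of 365, which leaves 169 later start days. Truly post-dose events dated pre-dose: (169×170/2) / (365×366/2) = 14,365/66,795 = 21.5%. In the other direction, truly pre-dose events dated on treatment: (195×196/2) / (364×365/2) = 19,110/66,430 = 28.8%.

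**4. Start day missing, onset fully dated, 30-day month.** Post-dose events falling before the 15th: 105/465 = 22.6%. Pre-dose events falling on or after the 15th: 120/435 = 27.6%. The mid-month start rule errs both ways. Together with step 2, this shows that the 1st-of-month rule is the main cause.

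**5. Tafamidis start and stop days both missing, same month.** Stop − start = 1 − 15 = −14 days, an impossible interval in the exposure sum.

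**6. Overall size, illustration only.** Assume a constant event rate, 1 to 5 years of exposure, and 5–20% of onset dates with a missing day. On average about half the start month is on treatment: 0.5/12 = 4.2% of one year, 0.5/60 = 0.8% of five. Affected share of adverse events: from 0.8% × 5% ≈ 0.04% to 4.2% × 20% ≈ 0.8%.

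**7. Effect of anchoring matching onsets to first dose.** Losses in steps 1 and 2 fall to zero. The share of all same-month partial onsets that are really pre-dose but counted as on treatment is (L−1)/(2L): 48.2% (L = 28), 48.3% (435/900, L = 30) and 48.4% (L = 31). For year-only onsets matched on year it is 66,430/133,225 = 49.9%.

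**The case against.** The strongest objection is about size. The 93–94% and 100% figures are conditional on a missing day and on the start month. If partial dates are rare, few events move, and a displaced adverse event can still be found in the all-enrolled listing. This stands, and it limits how much weight the point can carry.

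The loss of adverse events is also inferred. Treatment-emergent is undefined in the visible text, and the note closing SAP 8.2.6 gives only an upper limit, 28 days after last dose. This stands for adverse events. It does not reach symptoms, where 8.2.4 states the comparison with first dose outright. Patients already on tafamidis at enrollment are outside the point, because the start day does not set their window.

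Three stronger readings are tempting, and the documents do not support them.

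- A reader might infer that the rules always hide risk. Step 3 shows that the 15 July rule moves events both ways. A shortened exposure period reduces patient-years, which raises an exposure-adjusted rate.
- A reader might want partial stop dates moved to the end of the known period. In a 30-day month that replaces an average shift of 14.5 days early with one of 14.5 days late, which inflates exposure and lowers rates. Few stop-month events are lost now: a stop set to the 1st plus 28 days still reaches the 29th.
- A reader might add the birth-date rule, "For date of birth, if only year is collected, then the day and month will be considered as" 1 January. That overstates age by about half a year where only the year is held, but it affects neither treatment-emergence nor exposure. The protocol lists year of birth and SAP Table 2 lists date of birth, so how often the rule applies is unknown. It is a minor convention.

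**Conclusion.** The point holds in a limited form. As written, Section 7 places day-missing onsets in the start month before first dose by construction. For patients who start tafamidis after enrollment, those events then fall outside the treated window. The conditional shares in steps 1 and 2 rest on the literal rules. Step 2 also assumes uniform, independent days, and the result barely changes with month length. The impossible stop-before-start interval needs no assumption.

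The total effect cannot be computed, because the documents give no frequency of partial dates. The illustration puts it below 1% of adverse events, so it is unlikely to change the safety picture. It is still a systematic misclassification in main safety tables and is cheap to remove, so it should be corrected.

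**What to change.** Amend SAP Section 7, with matching changes in 8.2.4 and 8.2.6:

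1. When the known part of a partial onset or admission date matches the month (or year) of first dose, and nothing recorded shows an earlier onset, set the date to the first-dose date and count the event as treatment-emergent. Otherwise keep the present rule.
2. Define treatment-emergent as onset on or after first dose, and reword the symptom rule in 8.2.4 the same way. Without this, an onset set to the first-dose date would still fail the strict test there.
3. Do not allow an imputed stop date to precede the start date.
4. Report a sensitivity count of the affected events under the current rule.

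The 15th-of-month start rule can stay.

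The cost is a few lines of text, a change to the date derivation and one extra count, with no new data. The trade-off is that some pre-dose events will be counted as on treatment: up to about 48% of same-month partial onsets under the uniform assumption, and about half of year-only ones. The share is lower if adverse events are recorded only from first dose, as Protocol 11.2 provides. For a safety summary this is the more cautious error, and the sensitivity count shows how much it matters.

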## **8 STATISTICAL METHODOLOGY AND STATISTICAL ANALYSES**

### **8.1 STATISTICAL METHODS**

The key objectives of the survey are to better understand the natural history of ATTR (hereditary and wild-type forms) and the progression of disease in this patient population. Analysis of clinical outcomes will be conducted on all enrolled patients with available data. Outcomes will be examined separately for the untreated and tafamidis treated sets, as well as for appropriate subgroups within these set. Outcomes will include results of the key clinical, functional and QoL assessments used to define progression of disease.

Data will be summarized descriptively.

Continuous variables will be summarized using descriptive statistics ie, number of non-missing values and number of missing values [ie, n (missing)], mean, median, standard deviation (SD), minimum, maximum and 10th and 90th percentile.

Qualitative variables will be summarized by frequency counts and percentages. Unless otherwise specified, the calculation of proportions will be based on non-missing values.

In case the analysis refers only to certain visits, percentages will be based on the number of patients still present in the study at that visit, unless otherwise specified. Sample size in a subgroup needs to be at least 10 in order to have sufficient data to provide descriptive statistics, listings will be provided for smaller subgroups.

Kaplan-Meier estimates (product-limit estimates) will be presented including the median time with two-sided 95% confidence intervals (CIs), if the number of events are at least 5.

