**Table 1 Summary of ongoing tafamidis safety concerns to be addressed in THAOS**

Level of Risk or Missing Information	Specific Concerns
Important potential risks	Hepatotoxicity Reproductive and developmental toxicity and lactation Changes in thyroid function, particularly in pregnant women
Important missing information	Safety and efficacy in patients with ATTR-PN variants other than Val30Met (B3461029 substudy) CCI █ Patients with severe hepatic impairment

Note: The important identified risks (Urinary tract infections, Diarrhea, Upper abdominal pain and Vaginal infections); important potential risks (Hypersensitivity reactions); and missing information (Safety and efficacy in elderly patients and Longer-term safety) have been removed from the list of ongoing safety concerns from the tafamidis EU Risk Management Plan (RMP) Update (v 9.3), approved on 17 February 2020 and therefore will not be addressed in the final clinical study report (CSR) for THAOS.

All AE/SAE data will be collected for patients treated with commercially available tafamidis; patients receiving tafamidis as part of their participation in an open-label clinical study will have AE/SAE data collection through the open-label clinical study; reporting of Health Events of Interest will be available for patients not treated with tafamidis.

All visits are intended to be outpatient visits. Table 2 presents the data collected throughout a patient's participation in THAOS per the case report form (CRF). All assessments listed in Table 2 are recommended, but not required and will be determined by the investigator.

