### Electrocardiogram

For ECG, the following summaries will be provided at baseline and by yearly intervals:

- Any abnormalities in rhythm (Y/N)
- Sinus pause (Y/N)
- Atrial flutter (Y/N)

- Atrial fibrillation (Y/N)
- Atrial premature beat (Y/N)
- Junctional rhythm (Y/N)
- Ventricular tachycardia (Y/N)
- Ventricular premature complexes (Y/N)
- Other rhythm abnormality (Y/N)
- Pacemaker with normal function (Y/N)
- Low voltage (Y/N)
- Conduction abnormalities(Y/N)
- Types of conduction abnormalities
- Morphology abnormalities
- Types of morphology abnormalities
- Pathologic Q-Waves observed
- Types of P-Q wave abnormalities
- ST Segment T Wave abnormalities
- Types of ST Segment abnormalities

Also for the following parameters corresponding to ECG, summary statistics for the baseline and change from baseline by yearly intervals will be provided:

- QRS Axis
- PR
- QRS
- QT
- QTc

The summaries will be done using the tafamidis untreated set with predominantly cardiac or mixed phenotype at enrollment, tafamidis treated set with predominantly cardiac or mixed phenotype at enrollment, CCI [REDACTED] and either predominantly cardiac or mixed phenotype at enrollment, tafamidis treated set for patients who switched from predominantly neurologic to mixed phenotype and tafamidis untreated set for patients who switched from predominantly neurologic to mixed phenotype.

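### SAP 8.1 and SAP 7 give different denominators for visit-specific percentages, and the plan does not say which applies to the yearly ECG tables

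*SAP*

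**What the plan says.** SAP 7 sets the rule for missing data: "Patients with missing data for a variable will be excluded from the denominator when calculating proportions involving observed data for that variable". It also states that "Missing observations will be treated as missing except for dates".

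SAP 8.1 first agrees: "Unless otherwise specified, the calculation of proportions will be based on non-missing values". Its next paragraph then gives another base for analyses limited to particular visits: "percentages will be based on the number of patients still present in the study at that visit, unless otherwise specified".

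SAP 2.1, in the text after Table 1, makes testing discretionary: "All assessments listed in Table 2 are recommended, but not required and will be determined by the investigator". Protocol 9.3 says the same. SAP 2.1 (Assessments) and Protocol 9.1 also accept status updates for patients who have not come to the site.

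The visible output most clearly affected is in SAP 8.2.6, Electrocardiogram: "For ECG, the following summaries will be provided at baseline and by yearly intervals". Twelve of the listed items are marked as yes/no. They are tabulated for the treated and untreated sets with predominantly cardiac or mixed phenotype and for subgroups that change phenotype. That section names no denominator.

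**The concern.** The two rules give the same percentage only if everyone counted as present at a visit has a value for the variable. The study does not require that. Protocol 10.3 declares a patient lost to follow-up only when an annual visit is missed, contact cannot be made within a year of it, and status is unknown. The windows in SAP Appendix 2 are one year wide from Year 1 on. A patient can therefore be in the study for a whole window and have no ECG in it.

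Under the visit rule such a patient adds to the denominator and can never add to the numerator. The percentage then mixes two things: how often the finding occurs among those tested, and how often patients are tested. Disease progression is a key objective in SAP 8.1, which also examines the treated and untreated sets separately. Readers will compare percentages across years and between sets, and those comparisons would carry any difference in testing frequency.

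**Working it through.** The documents give no rate, assessed fraction or sample size for this point, so there is no stated figure to reproduce. The check is arithmetic on assumed inputs.

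**Inputs**
- *a*: fraction of patients present at a visit who have a value for the variable. Not in the documents; assumed 40% to 100%.
- *p*: share with the finding among those assessed. Not in the documents; assumed 20%, 40% and 60%.
- Rules: SAP 7 and the general sentence of 8.1 (non-missing), against the visit sentence of 8.1 (present).

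**Formulas**
- Non-missing rule: yes % = *p*; no % = 1 − *p*; sum 100%, whatever *a* is.
- Visit rule: yes % = *p* × *a*; no % = (1 − *p*) × *a*; sum = *a*.

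**Yes % under the visit rule**

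| *p* (also the non-missing result) | *a* = 40% | 50% | 60% | 80% | 100% |
|---|---|---|---|---|---|
| 20% | 8% | 10% | 12% | 16% | 20% |
| 40% | 16% | 20% | 24% | 32% | 40% |
| 60% | 24% | 30% | 36% | 48% | 60% |

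**What happens to unassessed patients.** Take 100 present, *a* = 50%, *p* = 40%, so 20 yes, 30 no and 50 without a value.
- Visit rule: yes 20/100 = 20%, no 30/100 = 30%, sum 50%.
- Non-missing rule: yes 20/50 = 40%, no 30/50 = 60%.
- Missing recoded as normal: yes 20/100 = 20%, no 80/100 = 80%.

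The visit rule gives the same yes percentage as recoding would, but a different no percentage.

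**Treated against untreated.** With *p* = 40% in both sets, 80% assessed in one and 50% in the other: 0.40 × 0.80 = 32% against 0.40 × 0.50 = 20%, a 12-point difference due to testing alone. The non-missing rule gives 40% in both.

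**Year against year.** With *p* = 60% throughout, 80% assessed in one year and 60% in another: 0.60 × 0.80 = 48% against 0.60 × 0.60 = 36%, again 12 points with no change in the finding.

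**If being present means having a recorded visit in the window.** Then *a* is the share of visiting patients who had the test. It would be nearer to 100%, but need not reach it, because each test is optional within a visit.

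**The case against.** The best reply is that the plan can be read as consistent. The visit sentence yields to any other specification, and Section 7 is an unqualified rule that could be that specification. The SAP's amendment table lists the handling of missing values for proportions as a deliberate update in Amendment 2, which suggests that Section 7 is the sponsor's latest intent. Being present at a visit could also mean only that patients who have left are dropped, with the non-missing rule applied to those who remain. Appendix 2 derives visits from assessment dates, which leans towards a narrow reading. It is also arguable whether a yearly series is an analysis limited to certain visits.

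This shows that the text is ambiguous, so a reader should not infer a settled intention to dilute the rates. It does not resolve the conflict. The general sentence of 8.1 carries the same yielding clause, so the visit sentence can equally be read as the exception to it, and a programmer could reasonably apply the more specific rule to a yearly table.

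Two stronger inferences are tempting and unsupported. One is that unassessed patients are counted as normal. No text says so; Section 7 leaves missing values missing, and under the visit rule such patients enter neither the yes nor the no count. The other is that ECG testing falls over time, so that stable disease would look like improvement. The documents say nothing on the trend in testing.

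Three mitigating points stand. Frequency counts accompany percentages, so the proportion among those assessed can be recovered where both yes and no counts are printed. Among the unredacted yearly outputs, the categorical one is the ECG list: laboratory and blood pressure outputs are changes from baseline, and echocardiography is summarised at baseline only. SAP 4 states that there are no hypotheses, so no test or decision depends on this. In a descriptive study, however, the percentages are themselves the result.

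**Conclusion.** The conflict between SAP 8.1 and SAP 7 is certain from the text; which rule the sponsor means to apply is not. If the visit rule were used for the yearly ECG summaries, each reported percentage would equal the percentage among those assessed times the fraction assessed. Differences in that fraction between years or between sets would then appear as differences in the finding. The mechanism follows from the stated rule and needs only that some patients present are unassessed, which the design permits. Its size rests wholly on assumed fractions and cannot be computed from the documents. The wording should be corrected, because a rule as stated can give a misleading table.

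**What to change.** Replace the visit sentence in SAP 8.1 with: *By-visit percentages use patients with a non-missing value of that variable in the visit window, as in Section 7; the number still in the study and the number assessed are shown beside each percentage.*

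This removes the undefined term from the denominator and brings 8.1 into line with Section 7. The added counts matter in their own right. A non-missing percentage describes only the patients tested, and the reader needs to see how many were not. That also serves Protocol 9.9, which names missing data as a threat to validity and refers its handling to the SAP. The cost is one SAP sentence and one extra row per table, with no new data collection.
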